8. MEASUREMENT OF EFFECT

Although response is not the primary endpoint of this trial, patients with measurable disease will be assessed by standard criteria. For the purposes of this study, patients should be re-evaluated with CT or MRI of the abdomen at 3-5 weeks after RT, and every 6 months for the first year.

8.1 Antitumor Effect – Solid Tumors

Response and progression will be evaluated in this study using the new international criteria proposed by the Response Evaluation Criteria in Solid Tumors (RECIST) Committee (Therasse, 2000). Changes in only the largest diameter (unidimensional measurement) of the tumor lesions are used in the RECIST criteria.

8.1.1 Definitions

Evaluable for toxicity. All patients will be evaluable for toxicity from the time of their first treatment with RT.

Evaluable for objective response. Only those patients who have measurable disease present at baseline and have had their disease re-evaluated will be considered evaluable for response. These patients will have their response classified according to the definitions stated below.

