4.3 Definition of Dose-Limiting Toxicity

The evaluation period of acute toxicity will be defined by the period of 28 days following the first fraction of RT. Dose Limiting Toxicity (DLT) will be defined according to Common Toxicity Criteria version 3.0 (See Appendix B) and includes the following acute toxicities:

- Grade 4 nausea (life-threatening consequences)
- Grade 4 skin toxicity (necrosis or ulceration of full thickness dermis, spontaneous bleeding from involved site)
- Grade 3+ liver toxicity including symptomatic ascites requiring invasive procedure, or total bilirubin $>3 \times$ ULN, or AST $>5 \times$ ULN, or ALT $>5 \times$ ULN that persists until day 28, and is attributable to radiation therapy.
- Grade 3+ enteritis (abdominal pain, fever, change in bowel habits with ileus, peritoneal signs) that is attributable to radiation therapy.

Patients must have a minimum of 3 weeks of follow-up after RT start for patient data to contribute enough follow-up for consideration of dose-limiting toxicity. However, any DLT that occurs with shorter follow-up will count towards the dose escalation rules. In addition, any grade 5 toxicity (i.e., death) considered possibly, probably or likely related to RT will be considered a DLT.

Any late toxicity that occurs beyond the 4 week period of evaluation will be closely followed and documented as a toxicity of interest. Included are the following severe late toxicities of RT:

- Grade 3+ gastrointestinal ulcer, fistula, stricture, or perforation (symptomatic and severely altered GI function, IV fluids or TPN ≥ 24 hrs, intervention indicated)
- Grade 3+ gastrointestinal mucositis (confluent ulcerations or pseudomembranes, bleeding with minor trauma)
- Grade 3+ gastrointestinal bleed (transfusion, interventional radiology or endoscopic or operative intervention)
- Grade 3+ gastrointestinal necrosis (inability to aliment adequately by GI tract, interventional radiology, intervention indicated)
- Grade 3+ liver toxicity including symptomatic ascites requiring invasive procedure, or total bilirubin $>3 \times$ ULN, or AST $>5 \times$ ULN, or ALT $>5 \times$ ULN, or asterixis, that is attributable to radiation therapy.

- Grade 3+ enteritis (abdominal pain, fever, change in bowel habits with ileus, peritoneal signs) that is attributable to radiation therapy.
- Grade 3+ pancreatitis (interventional radiology or operative intervention indicated)

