- Grade 3+ cholecystitis (interventional radiology or operative intervention indicated)

These severe, late toxicities will be evaluated between 1 and 12 months of therapy. There is no minimum follow-up time after RT start required for patient data to contribute enough follow-up for toxicities of interest.

Enrollment of 12 additional toxicity-evaluable patients at the MTD will provide a cohort of 18 patients at the putative MTD. If six or fewer of the 18 patients experience a toxicity of interest during the evaluation period, the combination will be considered tolerable. If 7 or more patients experience a toxicity of interest, the study committee will suspend accrual and determine whether further dose modifications are needed; the protocol will be amended accordingly. If the true probability of DLT at the MTD is 50%, the combination will be identified as too toxic with probability 0.88. If the true probability of DLT at the MTD is 25%, the combination will be identified as having an acceptable toxicity profile with probability 0.86.

Management associated with the above adverse events is outlined in Section 7.

Dose escalation will proceed within each cohort according to the following scheme. Dose-limiting toxicity (DLT) is defined above.

Number of Patients with DLT at a Given Dose Level	Escalation Decision Rule
0 out of 3	Enter 3 patients at the next dose level
≥ 2	Dose escalation will be stopped. This dose level will be declared the maximally administered dose (highest dose administered). Three (3) additional patients will be entered at the next lowest dose level if only 3 patients were treated previously at that dose.
1 out of 3	Enter at least 3 more patients at this dose level. 
 • If 0 of these 3 patients experience DLT, proceed to the next dose level. • If 1 or more of this group suffer DLT, then dose escalation is stopped, and this dose is declared the maximally administered dose. Three (3) additional patients will be entered at the next lowest dose level if only 3 patients were treated previously at that dose.
≤ 1 out of 6 at highest dose level below the maximally administered dose	This is generally the recommended phase 2 dose. At least 6 patients must be entered at the recommended phase 2 dose.

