4.5 Duration of Therapy

Duration of SBRT is to occur within a 10 day time period. Completion of the three fractions of RT will be delayed or foregone if:

- Intercurrent illness that prevents further administration of treatment,
- Further treatment is felt to be likely to result in severe and permanent impairment, or death (life-threatening toxicity),
- The patient decides to withdraw from the study, or
- General or specific changes in the patient's condition render the patient unacceptable for further treatment in the judgment of the investigator.

The use of chemotherapy after RT will be at the discretion of the treating physician.

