4.6 Duration of Follow Up

Patients will be followed on protocol for 12 months after initiation of RT or until death, whichever occurs first. Patients removed from protocol therapy for unacceptable adverse events will be followed until resolution or stabilization of the adverse event.

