4.7 Criteria for Removal from Study

Patients will be removed from study (but followed for potential of toxicity) when any of the criteria listed in Section 4.4 applies. The reason for study removal and the date the patient was removed must be documented in the Case Report Form.

5. Radiation Therapy Guidelines

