9. STATISTICAL CONSIDERATIONS

9.1 **Study Design/Endpoints**

The study is a phase I/II study that will escalate dose according to determination of dose limiting toxicities, in a 3+3 design as outlined in section 5.2. The MTD will be exceeded if 2 or more patients out of 6 (or a third or more) experience a DLT at that dose. The dose immediately below will be recommended for further study. . The phase II portion of the study will continue accrual at the maximum tolerated dose and measure the efficacy and health related quality of life after SBRT.

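### A patient who stops after one or two of three fractions without a listed DLT counts as DLT-free at the full dose level, which tilts the 3+3 toward escalation

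*Combined protocol and SAP*

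**What the plan says.** The primary objective (section 1.1) is the MTD of three fractions. The text that decides who counts toward it is spread over several sections.

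- **Who counts for escalation.** Section 4.3: "Patients must have a minimum of 3 weeks of follow-up after RT start for patient data to contribute enough follow-up". This is a condition on time, not on dose. The same section counts any DLT that occurs earlier, and any death judged at least possibly related to RT.
- **Who is evaluable for toxicity.** Section 8.1.1: "All patients will be evaluable for toxicity from the time of their first treatment with RT". Section 4.3 also uses the term for the expansion, "Enrollment of 12 additional toxicity-evaluable patients at the MTD will provide a cohort of 18 patients at the putative MTD", and 8.1.1 is the only place that defines it.
- **Incomplete treatment is foreseen.** Section 4.5: "Completion of the three fractions of RT will be delayed or foregone if" one of four conditions is met. They are intercurrent illness, feared severe toxicity ("Further treatment is felt to be likely to result in severe and permanent impairment, or death (life-threatening toxicity"), withdrawal, and a change in the patient's condition. Section 4.6 adds: "Patients removed from protocol therapy for unacceptable adverse events will be followed until resolution or stabilization of the adverse event".
- **Removed patients stay under observation.** Section 4.7: "Patients will be removed from study (but followed for potential of toxicity". It points to criteria in section 4.4, but the list that fits is in 4.5.
- **DLT list (section 4.3).** Grade 4 nausea, Grade 4 skin toxicity, Grade 3 or higher liver toxicity and enteritis (both attributable to RT), and RT-related death. Stopping RT is not on the list.
- **Decision limit (section 9.1).** "The MTD will be exceeded if 2 or more patients out of 6 (or a third or more) experience a DLT at that dose".

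No section sets a minimum number of fractions or says that a patient who stops early is replaced.

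**The concern.** Read together, these rules let a patient who received a third or two thirds of the prescription stand as evidence that the whole prescription is tolerated. At Level 3 (15 Gy x 3) such a patient has received 15 or 30 Gy of 45 Gy. The larger figure equals the full Level 1 total, and the smaller is below the 22.5 Gy of Level -1.

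Some of these stops would be caused by the treatment. Grade 3 nausea needing tube feeding or TPN (Appendix B) is not a DLT. Grade 3 pancreatitis appears in section 4.3 only among the late toxicities, beyond four weeks. A patient taken off RT for either one within the first 28 days is scored as having no DLT.

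Cohorts are three or six patients, so one patient can decide a row of the table: 0 of 3 escalates, 1 of 3 adds three more, 2 of 3 stops. The quantity at risk is the primary endpoint, and the error runs toward a higher dose, which then becomes the dose for the 18-patient cohort.

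**Working it through.** **1. The plan's own figures.** Section 4.3 gives operating characteristics only for the 7-of-18 rule. With X ~ Bin(18, 0.5), P(X >= 7) = 0.881 (stated 0.88). With X ~ Bin(18, 0.25), P(X <= 6) = 0.861 (stated 0.86). Both reproduce. The plan gives none for the 3+3, so they are derived here from its table.

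**2. Probability that a level clears.** Let p be the DLT rate in fully treated patients. A level clears with 0 of 3, or with 1 of 3 followed by 0 of 3.

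- All counted patients fully treated (equivalently, the stopped patient is replaced): (1-p)^3 + 3p(1-p)^5.
- One of the first three stopped early with no listed DLT and is counted: (1-p)^2 + 2p(1-p)^4.
- Same patient, stop counted as a DLT: (1-p)^5.

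At p = 1/3, the plan's own limit:

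- replaced: 0.2963 + 0.1317 = 0.428
- counted DLT-free: 0.4444 + 0.1317 = 0.576
- counted as a DLT: 0.132

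| True DLT rate p | As written | Replaced | Stop is a DLT |
|---|---|---|---|
| 0.20 | 0.804 | 0.709 | 0.328 |
| 1/3 | 0.576 | 0.428 | 0.132 |
| 0.50 | 0.312 | 0.172 | 0.031 |

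Every figure in the table is conditional on one such patient being among the first three.

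**3. Averaged over the chance of a stop.** The documents give no stop rate; f = 2%, 5% and 10% per patient are assumptions. At those rates a first cohort of three contains at least one stop with probability 1-(1-f)^3 = 0.059, 0.143 and 0.271. If stopped patients never show a DLT, the effective rate is p(1-f). If they carry half the risk, it is p(1-f/2). Putting these into the first formula at p = 1/3:

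| f | Effective p, no DLTs | Clears | Increase over 0.428 | Effective p, half risk | Clears | Increase |
|---|---|---|---|---|---|---|
| 2% | 0.327 | 0.441 | 0.01 | 0.330 | 0.434 | 0.01 |
| 5% | 0.317 | 0.461 | 0.03 | 0.325 | 0.444 | 0.02 |
| 10% | 0.300 | 0.494 | 0.07 | 0.317 | 0.461 | 0.03 |

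**4. The 18-patient rule.** If k stopped patients could have no late event, P(X >= 7) with X ~ Bin(18-k, 0.5) is 0.834, 0.773 and 0.696 for k = 1, 2 and 3, against 0.881. This bounds the loss from above. Three or more stops among 18 have probability 0.005, 0.06 and 0.27 at f = 2%, 5% and 10%.

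**The case against.** A reader might infer that any stop for toxicity is scored as DLT-free. The documents do not support that. Listed DLTs and RT-related deaths count after any number of fractions and with any length of follow-up. Appendix B gives perforation, bleeding, ischemia and necrosis as examples of Grade 4 enteritis, so much of what would count as life-threatening under section 4.5 is already a DLT. A patient with under three weeks of follow-up and no DLT is not counted at all. What remains is stops for unlisted events, stops for feared toxicity, and stops unrelated to RT.

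The result is also drawn from silence. The sentence in 8.1.1 sits in the tumour-response section and says nothing about escalation; section 4.3 governs. Section 4.7 could be read as taking removed patients out of the escalation count. That does not rescue the plan: toxicity stops would then drop out of the evidence, and the table has no row for a cohort of two.

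The content of the DLT list is a separate design choice that affects fully treated patients too. The nausea threshold may be deliberate: section 2.2 reports that about 63% of patients in the earlier 15 Gy x 3 study had Grade 2 or higher symptoms before treatment. That stands, and this point does not ask for Grade 3 nausea to become a DLT in patients who complete RT.

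The weekly safety review in section 6 would bring toxicity stops to attention, but no rule says how to count them.

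**Conclusion.** The point holds in this limited form: a patient who stops early without a listed DLT and reaches three weeks is counted as DLT-free at the three-fraction level, and this favours escalation. At p = 1/3 the chance of clearing the level is 0.58 instead of 0.43 when one such patient is among the first three and the rest are fully treated. Averaged over assumed stop rates of 2% to 10%, the increase is about 0.01 to 0.07 if stopped patients never show a DLT, and 0.01 to 0.03 if they carry half the risk. The averaged figures also assume that stopping is unrelated to a patient's DLT risk at full dose.

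Two larger readings are tempting. The contrast of 0.58 with 0.13 applies only to a stop that is itself caused by toxicity; three of the four reasons in section 4.5 need not be. The fall from 0.88 to 0.70 in the expansion needs three stops and no late risk at all in those patients. Neither should be taken as the expected effect.

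The average effect is modest, but it bears on the primary endpoint, it runs toward the higher dose, and it is cheap to remove. It should be corrected.

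**What to change.** In section 4.3:

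- Define DLT-evaluable for escalation as any patient with a DLT, or a patient who received all three fractions and completed the DLT follow-up.
- Add to the DLT list the omission of fraction 2 or 3 because of toxicity attributable to RT. This is the standard the section already uses for liver toxicity and enteritis. Without this item, replacement would drop toxicity stops from the evidence.
- Replace patients who stop for other reasons without a DLT, and keep them in all toxicity summaries.

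In section 8.1.1, limit evaluability from first treatment to toxicity reporting.

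Leave the 7-of-18 rule on all treated patients and report the three-fraction subset beside it. Restricting that rule to patients with three fractions or an event would admit part-dose patients only when they had an event, and so push the observed rate upward. In escalation the same asymmetry is acceptable, because a DLT on part of the dose is evidence against the whole.

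Dose levels, planning limits and 3+3 thresholds stay as they are. The reason for and date of removal are already recorded (section 4.7), so no new procedure is needed. Each replacement adds one patient, about two to four weeks at 1-2 per month, and the ceiling of 24 needs a small allowance. The downside is that a cautious stop attributed to RT may end escalation earlier.

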8.1.2 Disease Parameters

Measurable disease. Measurable lesions are defined as those that can be accurately measured in at least one dimension (longest diameter to be recorded) as ≥ 10 mm with CT or MRI. All tumor measurements must be recorded in millimeters (or decimal fractions of centimeters).

Non-measurable disease. All other lesions (or sites of disease), including small lesions (longest diameter <20 mm with conventional techniques or <10 mm using spiral CT scan), are considered non-measurable disease.

Target lesions. The primary lesion (with immediately adjacent lesions) that will be treated with RT should be identified as the **target lesion(s)** and recorded and measured at baseline. Target lesions should be selected on the basis of their size (lesions with the longest diameter) and their suitability for accurate repeated measurements (either by imaging techniques or clinically). A sum of the longest diameter (LD) for all target lesions will be calculated and reported as the baseline sum LD. The baseline sum LD will be used as reference by which to characterize the objective tumor response.

8.1.3 Methods for Evaluation of Measurable Disease

All measurements should be taken and recorded in metric notation using a ruler or calipers. All baseline evaluations should be performed as closely as possible to the beginning of treatment and never more than 4 weeks before the beginning of the treatment.

The same method of assessment and the same technique should be used to characterize each identified and reported lesion at baseline and during follow-up.

CT and MRI These techniques should be performed with cuts of 5 mm or less in slice thickness contiguously.

8.1.4 **Response Criteria**

8.1.4.1 **Evaluation of Target Lesions**

Complete Response (CR): Disappearance of the primary target lesion(s)

Partial Response (PR): At least a 30% decrease in the sum of the longest diameter (LD) of target lesions, taking as reference the baseline sum LD

Progressive Disease (PD): At least a 20% increase in the sum of the LD of target lesions, taking as reference the smallest sum LD recorded since the treatment started or the appearance of one or more new lesions

Stable Disease (SD): Neither sufficient shrinkage to qualify for PR nor sufficient increase to qualify for PD, taking as reference the smallest sum LD since the treatment started

9. STATISTICAL CONSIDERATIONS

9.1 **Study Design/Endpoints**

The study is a phase I/II study that will escalate dose according to determination of dose limiting toxicities, in a 3+3 design as outlined in section 5.2. The MTD will be exceeded if 2 or more patients out of 6 (or a third or more) experience a DLT at that dose. The dose immediately below will be recommended for further study. . The phase II portion of the study will continue accrual at the maximum tolerated dose and measure the efficacy and health related quality of life after SBRT.

9.2 Sample Size/Accrual Rate

The study will accrue 18 patients at the putative maximum tolerated dose, giving a sample size of up to 24 patients. Accrual will likely be 1-2 patients per month. Toxicities of interest that occur within the 1-12 month time frame after RT start will be documented. For further detail regarding modification of enrollment or dose escalation based on late toxicities of interest, see section 5.2.

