**A STUDY OF STEREOTACTIC BODY RADIATION THERAPY
IN PATIENTS WITH UNRESECTED CARCINOMA
OF THE PANCREAS OR AMPULLA**

Coordinating Center:
University of Chicago Medical Center

[figure not shown]
Principal Investigator:
[name].
Department of Radiation and Cellular Oncology
[name]
[name]
[contact]
[contact]
[contact]

Co-Investigators:
Department of Radiation and Cellular Oncology
[name].
[name].
[name].

Department of Medicine, Section of Hematology/Oncology
[name].
[name].
[name].
[name].

Department of Surgery
[name].
[name].

SCHEMA

Patient Population: (see section 3.0 for complete eligibility)

- Biopsy-proven unresected cancer of the pancreas or ampulla
- No prior complete surgical resection
- ECOG performance status ≤ 2
- No prior history of radiation therapy to the abdominal area
- Primary tumor size ≤ 7.5 cm in largest diameter
- No duodenal invasion
- Patients with metastatic disease may be included if local symptoms are present

Required Sample Size: upto 24 patients, with 1-2 patients accrued per month

Study Center: University of Chicago Medical Center, Pritzker School of Medicine

Concept and Rationale: Cancers involving the upper gastrointestinal tract often present at advanced stages, and as such, are associated with an overall survival that may be less than one year after diagnosis. Because these cancers may progress both locally and distantly, a standard of care for unresected, non-metastatic disease is to administer both Radiation Therapy (RT) and systemic chemotherapy. Typically, radiation therapy is given concurrently with radiosensitizing chemotherapy using conventional fraction sizes (1.8-2 Gy/fraction), requiring 5-6 weeks of treatment.

In recent years, the ability to more precisely target and treat disease with RT has sparked interest in delivering larger fraction sizes (e.g., > 8 Gy/fraction), thereby reducing treatment time, and perhaps improving biologic effect. For other sites such as the lung and liver, this form of therapy (known as Stereotactic Body Radiation Therapy) has achieved high rates of local control, with no appreciable increase in toxicity of treatment in the observed time of follow-up.

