Statistical Methods: A 3+3 dose escalation design will be used. The maximum tolerated dose will be exceeded if 2 or more patients out of 6 (or a third or more) experience a dose limiting toxicity (DLT) at that dose. The dose immediately below will be recommended for further study. DLTs are defined as any acute toxicity of Grade 4 nausea, Grade 4 skin toxicity, Grade 3+ liver toxicity (metabolic or ascites), or Grade 3+ enteritis. Severe late toxicities of interest (occurring beyond the 4 week period of evaluation and up to 12 months after RT) will include any Grade 3+ gastrointestinal toxicity (such as small bowel ulcer, stricture, perforation, bleed, liver damage, pancreatitis, or cholecystitis). If the rate of any severe late toxicity of interest exceeds 25% (i.e., 7 or more patients in the expanded cohort of 18 treated at the MTD), the study committee will suspend accrual and determine whether further dose modifications are needed; the protocol will be amended accordingly.

TABLE OF CONTENTS

SCHEMA	ii
1. OBJECTIVES	1
1.1. Primary Objectives	1
1.2. Secondary Objectives	1
2. BACKGROUND	1
2.1 Unresectable carcinoma of the pancreas	1
2.2 Rationale	1
3. PATIENT SELECTION	3
3.1 Eligibility Criteria	3
3.2 Exclusion Criteria	3
3.3 Inclusion of Women and Minorities	4
4. TREATMENT PLAN	4
4.1 Radiation Therapy dose escalation	4
4.2 Measuring Health Related Quality of Life	4
4.3 Definition of Dose-Limiting Toxicity	5
4.4 General Concomitant Medication and Supportive Care Guidelines	7
4.5 Duration of Therapy	7
4.6 Duration of Follow Up	8
4.7 Criteria for Removal from Study	8
5. RADIATION THERAPY GUIDELINES	8
5.1 Treatment related planning procedures	8
5.2 RT planning parameters	8
5.3 RT Treatment	10
6. ADVERSE EVENTS	10
7. STUDY CALENDAR	133
8. MEASUREMENT OF EFFECT	144
8.1 Antitumor Effect – Solid Tumors	144
9. STATISTICAL CONSIDERATIONS	155
9.1 Study Design/Endpoints	155
9.2 Sample Size/Accrual Rate	166
9.3 Analysis of Secondary Endpoints	166
10. CONFIDENTIALITY	166
10.1 Patient confidentiality issue	17
REFERENCES	18
APPENDIX A	20
APPENDIX B	21
APPENDIX C	22
APPENDIX D	23

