5.2 RT Planning Parameters

- 5.2.1. The definition of volumes will be in accordance with the ICRU Report 62: Prescribing, Recording and Reporting Photon Beam Therapy. (ICRU, 1999)
- 5.2.1.1. A gross tumor volume (GTV) will be entered for each lesion, based on available imaging data.
- 5.2.1.2. In the absence of respiratory gating, an internal target volume (ITV) will be defined as the volume that accounts for intrafraction target motion.
- 5.2.1.3. A clinical target volume (CTV) will be defined as the GTV or ITV (when available) plus a margin for microscopic extension.
- 5.2.1.4. A planning target volume (PTV) will be determined which will correspond to CTV plus appropriate margin for tumor motion and set-up uncertainty.
- 5.2.2. 3D coplanar or non-coplanar beam arrangements will be custom designed for each case to deliver highly conformal prescription dose distributions. The treatment plan used for each patient will be based on an analysis of the volumetric dose, including dose volume histogram of the PTV and normal structures. 3D “forward” planning or “inverse” planning with beamlet intensity modulated treatment planning are allowed.
- 5.2.3. Treatment is to be delivered using a linear accelerator and photon energies ≥ 6 MV.
- 5.2.4. Corrections will be made to account for tissue heterogeneity.
- 5.2.5. RT is to be delivered to each site in 3 fractions over a period of up to 10 total days.
- 5.2.6. RT Dose: A phase I escalation of doses will be performed in order to determine in MTD in Gy. Doses of radiation will start at Level 1 and increase as follows in order to determine the MTD in Gy:
 - Level 1: 10 Gy/ fraction \times 3 fractions = 30 Gy

Level 2: 12.5 Gy/fraction x 3 fractions = 37.5 Gy

Level 3: 15 Gy/fraction x 3 fractions = 45 Gy

If DLT is met at Level 1, dose will be de-escalated to Level -1: 7.5 Gy x 3 fractions = 22.5 Gy

5.2.7. Doses will be prescribed to the PTV. The PTV may be covered by a lower isodose line than usually used in conventional radiotherapy planning, typically around 80% but ranging from 60-100%. Ideally, the prescription dose will cover >90% of the GTV (V100 GTV > 90%, and V95PTV > 90%). A lower coverage goal (with no minimum requirement of PTV coverage) will be acceptable if necessary to meet normal tissue constraints, which will be assigned priority over tumor coverage.

5.2.7.1. Any dose > 110% must be within the PTV.

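### The stated maximum of 24 patients is not a maximum: with 18 at the MTD, the protocol's own escalation rules also lead to 27 or 30

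*Combined protocol and SAP*

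**What the plan says.** Section 9.2 derives the total from the MTD cohort: "The study will accrue 18 patients at the putative maximum tolerated dose, giving a sample size of up to 24 patients". The Schema gives the same limit: "Required Sample Size: upto 24 patients, with 1-2 patients accrued per month".

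The cohort of 18 is built in Section 4.3 from six escalation patients plus twelve more: "Enrollment of 12 additional toxicity-evaluable patients at the MTD will provide a cohort of 18 patients at the putative MTD". The Schema ties the late-toxicity trigger to that size ("7 or more patients in the expanded cohort of 18 treated at the MTD"). Section 4.3 gives the rule's operating characteristics as 0.88 (called too toxic at a true rate of 50%) and 0.86 (called acceptable at 25%).

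The use of patients at each level is set by the following rules:

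- After no DLT in three, escalation continues with three patients used at that level.
- After one DLT in three: "Enter at least 3 more patients at this dose level". If none of these has a DLT, escalation continues with six used; otherwise it stops.
- After a stop, the next lower level is filled from three to six.
- At the selected dose: "At least 6 patients must be entered at the recommended phase 2 dose".
- Section 9.1: "The MTD will be exceeded if 2 or more patients out of 6 (or a third or more) experience a DLT at that dose".
- Section 5.2.6 adds a fourth level: "If DLT is met at Level 1, dose will be de-escalated to Level -1".

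**The concern.** A limit of 24 with 18 at the MTD allows six patients in total at all other levels. That is enough for two other levels at three patients each, or one other level at six. The design has three planned levels and a de-escalation level, and any of them can take six. The figure of 24 therefore looks like one particular path rather than an upper limit.

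On any path that needs 27 or more, the two commitments cannot both be kept, and no section says which gives way. Either enrolment runs past the stated total, or the MTD cohort falls below the 18 on which the seven-event late-toxicity rule was calibrated. The conflict would surface mid-trial, and on many of these paths only after DLTs have used up the spare places.

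**Working it through.** **Inputs.** 18 at the MTD (Sections 4.3 and 9.2); three or six patients at each other opened level (table in Section 4.3); two or more DLTs in three or in six stops a level (Sections 4.3 and 9.1); Levels 1, 2, 3 and -1 (Sections 4.1 and 5.2.6).

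**Formula.** Total at full accrual = 18 + patients at all other opened levels.

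**Where 24 comes from.** With all three levels open, 3 + 3 + 18 = 24: no DLT in three at Levels 1 and 2 with the MTD at Level 3, or Level 3 stopped after three patients with the MTD at Level 2. With one other level open, 6 + 18 = 24.

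**Paths beyond 24 that need no outside figure.**

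- Level 1 at 1/6, Level 2 at 0/3, MTD Level 3: 6 + 3 + 18 = 27.
- Levels 1 and 2 both at 1/6, MTD Level 3: 6 + 6 + 18 = 30.
- Level 1 at 0/3, Level 3 stopped at six, MTD Level 2: 3 + 6 + 18 = 27.
- Level 1 at 1/6, Level 3 stopped at six, MTD Level 2: 6 + 6 + 18 = 30.

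**All reachable totals.**

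| MTD | Highest level opened | Totals |
|---|---|---|
| Level 3 | 3 | 24, 27, 30 |
| Level 2 | 3 | 24, 27, 30 |
| Level 1 | 2 | 21, 24 |
| Level 1 | 3 | 27, 30 |
| Level -1 | 1 | 21, 24 |
| Level -1 | 2 | 27, 30 |
| Level -1 | 3 | 33, 36 |
| None declared | any | 6 to 24 |

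**How often.** For a common DLT rate p, a level is passed with three patients with probability a = (1-p)^3 and with six with probability b = 3p(1-p)^5. At p = 5%, a = 0.8574 and b = 0.1161. Level 3 qualifies with at most one DLT in six: 0.9672. For an MTD at Level 3:

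- P(24) = a² × 0.9672 = 0.711
- P(27) = 2ab × 0.9672 = 0.193
- P(30) = b² × 0.9672 = 0.013

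That gives 0.206 above 24. Paths ending at a lower MTD add 0.025, so P(total > 24) = 0.231. The same exact calculation over all paths gives:

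| Assumed DLT rates | P(>24) | P(30 or more) |
|---|---|---|
| flat 1% | 0.057 | 0.001 |
| flat 2% | 0.109 | 0.003 |
| flat 3% | 0.155 | 0.007 |
| flat 5% | 0.231 | 0.016 |
| flat 10% | 0.334 | 0.044 |
| Levels 1/2/3 at 5/10/15% (Level -1 at 2.5%) | 0.351 | 0.036 |
| 10/15/25% (5%) | 0.414 | 0.075 |
| 15/25/40% (10%) | 0.325 | 0.083 |

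P(total > 30) is at most 0.0017. Among trials that open all three levels and declare an MTD, the share above 24 is 6% (flat 1%), 24% (flat 5%), and 40%, 56% and 64% on the three rising curves.

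**If 24 were enforced by shrinking the cohort.** A path to 27 leaves 24 - 9 = 15 at the MTD; a path to 30 leaves 24 - 12 = 12. The plan's own figures reproduce at 18: P(X ≥ 7 | 18, 0.5) = 0.881 and P(X ≤ 6 | 18, 0.25) = 0.861.

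| MTD cohort | Threshold | P(flag at 50%) | P(acceptable at 25%) |
|---|---|---|---|
| 18 | 7 | 0.881 | 0.861 |
| 15 | 7 kept | 0.696 | 0.943 |
| 12 | 7 kept | 0.387 | 0.986 |
| 15 | 6 (scaled) | 0.849 | 0.852 |
| 12 | 5 (scaled) | 0.806 | 0.842 |

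Cohorts of 9 and 6 (the paths to 33 and 36) would give 0.090 and 0 at 50% with the threshold kept at seven, but those paths are very rare.

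**Accrual.** At one to two patients per month, 24 patients take 12 to 24 months, 27 take 13.5 to 27, and 30 take 15 to 30.

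**The case against.** The best defence is that 18 is the firm number and 24 a planning figure built as 3 + 3 + 18. On that reading the consequence is modest. The overrun is usually three patients (for example 0.339 of the 0.414 at 10/15/25%), the primary objective is the MTD, and no powered comparison depends on the total. This is a fair guess at the intent, but the documents do not say it: both places give the number as an upper limit.

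Two further points stand in part. The steep fall in the chance of flagging needs both a smaller cohort and an unchanged threshold of seven, and no section prescribes either. The Schema also expresses the trigger as a rate above 25%, so a smaller cohort would naturally get a smaller count, and with 6 of 15 or 5 of 12 the loss is small. Totals of 33 and 36 need repeated step-downs that the table does not spell out, as does an MTD at Level 1 after Level 3 has opened. The finding needs only 27 and 30 with the MTD at Level 2 or 3, which follow directly from the table.

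Finally, the percentages rest on assumed DLT rates. They show that the overrun is not a remote possibility; they do not estimate its frequency in this trial.

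**Conclusion.** The concern holds. Under the written rules 24 is one of several possible totals. It is the minimum, not the maximum, once all three planned levels open and an MTD is declared. The maximum is 30 with the MTD at Level 1, 2 or 3, and 36 in the very rare case of de-escalation to Level -1 after all levels have opened.

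Under the assumed DLT rates 24 is exceeded in 6% to 41% of trials, so it is enough in 59% to 94%. These results read the instruction to add at least three as exactly three, fill Level -1 as three then three, reapply the stopping rule at each lower level, run accrual to completion and replace no patient. Adding more than three at a level, or replacing patients, would raise the totals.

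The error is confined to the stated total and its unresolved conflict with the cohort of 18.

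**What to change.** In the Schema and Section 9.2, replace the limit with: up to 30 patients if the MTD is Level 1, 2 or 3; up to 36 in the rare case of de-escalation to Level -1 after all levels have opened; fewer if no MTD is declared; all before any replacement of non-evaluable patients. This changes one number in two places and permits nothing that the written rules do not already allow. The plan states an accrual rate and no duration, so the rate can stay, but any timeline built on 24 should be extended to the 15 to 30 months that 30 patients imply.

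If 24 is meant as a hard cap, say so. State that the MTD cohort may then fall below 18 (usually to 15 or 12, rarely to 9 or 6), and give the late-toxicity threshold with its operating characteristics for each size. That costs a short table in Section 4.3 and a matching line in the Schema.

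Either way, state which of the two numbers governs. No dose, DLT definition or escalation rule needs to change.
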